5.3 Regression Analysis

We will perform different regression analyses to test the hypotheses listed above. Because our data contains many possible control variables, we will use a double-lasso procedure to select regression controls. We will also include a control for whether the participant's availability to participate in a

follow up survey (as indicted at baseline). These control variables are denoted as X in the regression specifications below.

Unless otherwise noted, we will examine treatment effects on knowledge of COVID symptoms, knowledge of COVID transmission, intended donation to a COVID-related charity, willingness to pay for masks, changes in reported behavior. In what follows, we present the minimal regressions to test each of the hypotheses, restricting to the smallest subset of treatments. However, we could also execute the same tests in the full sample, but with more treatment interactions.³

Note that the “COVID” indicator covers cases when doctors mention COVID plus racism, or COVID alone. In text, we refer to this group as the treatment group.

1. Baseline treatment effect: does any of the COVID-19 messaging affect knowledge, intended behavior, priorities in donation, or actual behavior?

- Question: does COVID messaging from doctors have any effect?

Samples: separate analysis for all respondents, black respondents, and white respondents.

Regression:

$$Y = \beta \cdot \text{COVID Video} + X'\gamma + \epsilon$$

2. Does racial concordance of the doctor in the COVID-19 video change the effectiveness for messaging?

- Question: Bolded, immediately above.

Samples: COVID video groups. Separate analysis for black and white respondents.

Regression:

$$Y = \beta \cdot \text{DocConcord} + X'\gamma + \epsilon$$

Alternate Specification: To allow, for a level effect of doctor concordance, we can also run the following modified regression, including both the COVID video and control groups.

$$Y = \beta \cdot \text{DocConcord} \cdot \text{COVID Video} + \alpha \cdot \text{COVID Video} + \delta \cdot \text{DocConcord} + X'\gamma + \epsilon$$

- Question: Bolded above, but using an alternate definition of concordance. We'll require a) all messengers or b) any messenger to concord with the respondent's race.

For any outcomes where β is of the same sign for white and black respondents, we will estimate the above equation again in the full sample.

3. Does the AMA racism acknowledgment affect the impact of messaging on any outcomes? Does it change the concordance effect?

³In some cases, especially when including controls, these full-sample tests may be preferable to these stripped-down regressions.

- Question: Does the AMA racism messaging heighten or dull COVID messaging from doctors?

Samples: COVID video groups. Separate analysis for all respondents, black respondents, and white respondents.

Regression:

$$Y = \beta \cdot \text{AMARacism} + X'\gamma + \epsilon$$

Alternate Specification: To allow, for a level effect of the AMA racism message, we can also run the following modified regression, including both the COVID video and control groups.⁴

$$Y = \delta \cdot \text{AMARacism} \cdot \text{COVID Video} + \alpha \cdot \text{COVID Video} + \beta \cdot \text{AMARacism} + X'\gamma + \epsilon$$

- Question: Does the AMA racism acknowledgment heighten or dull any doctor concordance effects?

Samples: COVID video groups. Separate analysis for black and white respondents.

Regression:

$$Y = \delta \cdot \text{AMARacism} \cdot \text{DocConcord} + \alpha \cdot \text{AMARacism} + \beta \cdot \text{DocConcord} + X'\gamma + \epsilon$$

Alternate Specification: Again, we can also run the following modified regression, including both the COVID video and control groups.

$$Y = \delta \cdot \text{DocConcord} \cdot \text{AMARacism} \cdot \text{COVID Video} + \lambda \cdot \text{AMARacism} \cdot \text{COVID Video} + \phi \cdot \text{DocConcord} \cdot \text{COVID Video} + \rho \cdot \text{AMARacism} \cdot \text{DocConcord} + \alpha \cdot \text{COVID Video} + \beta \cdot \text{AMARacism} + \psi \cdot \text{DocConcord} + X'\gamma + \epsilon$$

4. Does concordance of the AMA messenger matter?

- Question: Does a race-concordant AMA messenger delivering a message about racial injustice make COVID messaging from doctors more or less effective, relative to a race-discordant AMA messenger?

Samples: Individuals receiving an AMA message about racial injustice and a treatment message about COVID. Separate analysis for black and white respondents.

Regression:

$$Y = \beta \cdot \text{AMAConcord} + X'\gamma + \epsilon$$

Alternate Specification: We can also run the following modified regression, the COVID video and control groups, with both types of AMA messages.

$$Y = \delta \cdot \text{COVID Video} \cdot \text{AMAConcord} \cdot \text{AMARacism} + \lambda \cdot \text{AMAConcord} \cdot \text{AMARacism} + \rho \cdot \text{AMAConcord} \cdot \text{COVID Video} + \psi \cdot \text{COVID Video} \cdot \text{AMARacism} + \alpha \cdot \text{AMAConcord} + \beta \cdot \text{AMARacism} + \phi \cdot \text{COVID Video} + X'\gamma + \epsilon$$

⁴Ex ante, we think that an AMA level effect in the control group is more likely than a doctor concordance level effect. However, we include all alternates for completeness. These alternate specifications including the control group are relevant in the presence of a level effect.

- Question: Does a race-concordant AMA messenger make COVID messaging from a race-concordant doctor more or less effective, when delivering the AMA message about racial injustice?

Samples: COVID video groups receiving the AMA message about racism. Separate analysis for black and white respondents.

Regression:

$$Y = \delta \cdot \text{AMAConc} \cdot \text{DocConc} + \alpha \cdot \text{AMAConc} + \beta \cdot \text{DocConc} + X'\gamma + \epsilon$$

Alternate Specification: We can also run the following modified regression, the COVID video and control groups, with both types of AMA messages.

$$Y = \delta \cdot \text{AMAConc} \cdot \text{AMARacism} \cdot \text{DocConc} \cdot \text{Covid Video} \\ + \alpha_1 \cdot \text{DocConc} \cdot \text{AMARacism} \cdot \text{COVID} + \alpha_2 \cdot \text{DocConc} \cdot \text{AMARacism} \cdot \text{AMAConc} \\ + \alpha_3 \cdot \text{DocConc} \cdot \text{COVID} \cdot \text{AMAConc} + \alpha_4 \cdot \text{AMARacism} \cdot \text{COVID} \cdot \text{AMAConc} \\ + \beta_1 \cdot \text{DocConc} \cdot \text{AMARacism} + \beta_2 \cdot \text{DocConc} \cdot \text{COVID} + \beta_3 \cdot \text{DocConc} \cdot \text{AMAConc} \\ + \beta_4 \cdot \text{AMARacism} \cdot \text{COVID} + \beta_5 \cdot \text{AMARacism} \cdot \text{AMAConc} + \beta_6 \cdot \text{COVID} \cdot \text{AMAConc} \\ + \rho_1 \cdot \text{DocConc} + \rho_2 \cdot \text{AMARacism} + \rho_3 \cdot \text{AMAConc} + \rho_4 \cdot \text{COVID} + X'\gamma + \epsilon$$

5. **What are the effects of acknowledging racial disparities in COVID incidence?** In addition to the typical set of outcomes, we will also analyze effects on allocated donations to black-specific versus race-agnostic COVID-related charities.

- Question: what is the main effect of acknowledging racial disparities of COVID incidence?

Samples: treated respondents only. Separate analysis for black, white, and all respondents.

Regression:

$$Y = \beta \cdot \text{Vid2RacialDisp} + X'\gamma + \epsilon$$

- Question: are race-concordant doctors more effective messengers about racial disparity?

Samples: treated respondents only. Separate analysis for black, white, and all respondents.

Regression:

$$Y = \delta \cdot \text{DocConc} \cdot \text{Vid2RacialDisp} + \alpha \cdot \text{Vid2RacialDisp} + \beta \cdot \text{DocConc} + X'\gamma + \epsilon$$

- Question: does acknowledging widespread racism alter the effectiveness of later discussing racial disparities in COVID?

Samples: treated respondents only. Separate analysis for black, white, and all respondents.

Regression:

$$Y = \delta \cdot \text{AMARacism} \cdot \text{Vid2RacialDisp} + \alpha \cdot \text{Vid2RacialDisp} + \beta \cdot \text{AMARacism} + X'\gamma + \epsilon$$

- Question: does a race-concordant AMA messenger's prefacing statement have a different amplifying effect than a race discordant AMA messenger? That is, if doctors are going to discuss racial disparities in COVID and we're going to preface this with the AMA racism statement, do we expect different results if the statement comes from a concordant versus discordant AMA messenger?

Samples: Must have seen *both* a COVID video *and* an AMA racism video. Separate analysis for black and white respondents.

Regression:

$$Y = \delta \cdot \text{AMAConcord} \cdot \text{Vid2RacialDisp} + \alpha \cdot \text{Vid2RacialDisp} + \beta \cdot \text{AMAConcord} + X'\gamma + \epsilon$$

Alternate specification: restrict sample to those seeing a COVID video, include both types of AMA messages. Regression:

$$Y = \delta \cdot \text{AMARacism} \cdot \text{AMAConcord} \cdot \text{Vid2RacialDisp} + \lambda \cdot \text{AMAConcord} \cdot \text{Vid2RacialDisp} + \rho \cdot \text{AMAConcord} \cdot \text{AMARacism} + \phi \cdot \text{AMARacism} \cdot \text{Vid2RacialDisp} + \alpha \cdot \text{Vid2RacialDisp} + \beta \cdot \text{AMAConcord} + \psi \cdot \text{AMARacism} + X'\gamma + \epsilon$$

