5.2 Key Outcomes

We intend to measure the treatment effects on the following set of outcomes:

1. The number of participants with knowledge of COVID related symptoms and transmission as assessed by a questionnaire we've developed specifically relevant to the intervention videos we are using for the project. Specifically, we define the following three outcomes, measured both at first contact and followup:

- Knowledge of COVID symptoms: participants are asked to identify 4 symptoms of COVID from a list of 9. We will define an indicator for whether participants select the 3 most common symptoms (fever, cough, difficulty breathing).
 - Knowledge of COVID prevention: participants are asked to identify 3 COVID prevention behaviors from a list of 7. We will define an indicator for whether participants select the 3 behaviors emphasized in the videos (staying outside and 6ft from others; washing hands when going and coming from home; mask wearing).
 - Knowledge of asymptomatic infection: an indicator for whether participants correctly answer that COVID can spread asymptotically.
2. Behavioral outcome 1: Number of participants who report behavior change related to messages provided in the intervention videos; measured via a specific questionnaire instrument we've developed to correspond to the intervention. Specific behaviors include physical distancing, mask wearing, and hand hygiene. Since we ask about several safety behaviors, we will define a standardized index to combine them into one measure, calculated at both first contact and endline. The key outcome is the within-person change in this safety index from first contact to endline.
 3. Behavioral outcome 2: Revealed preference estimate of willingness to pay for masks. The subjects will trade-off the willingness to get a pair of masks or an amazon gift card when participating in a strategy-proof lottery.
 4. Behavioral outcome 3: Number of links people click on for additional information on the COVID-19 behaviors. Links will include testing locations, state public health hotline, and symptom tracker.
 5. Behavioral outcome 4: Donations to a COVID-related charity. After providing information on the number of weekly COVID cases, we are measuring the willingness to donate to a COVID-related charity vs. a generic health-related charity.

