We intend to compare the results of our hypothesis tests separately for the time period before the Jacob Blake police shooting in Kenosha, WI on August 23, 2020, and the time period after. We propose to do this for two reasons. First, we launched the study at a time when the large-scale protests from earlier in the summer following the murder of George Floyd had somewhat ebbed. So the events in Kenosha may bring issues of racial injustice to the fore. Second, and perhaps more importantly, polarization surrounding the narrative of the protests has markedly increased following the events of Kenosha. Several speakers at the Republican National Convention explicitly discussed the violent component of the protests, for example, and both candidates for the US presidency are making trips to Kenosha. This increased polarization is likely to have the most relevance for the white respondents in our study, and may enhance any differential response we find by political affiliation. We propose to split the sample into the period before August 23, 2020 and the period following August 26, 2020. We will omit surveys collected on days in the interim when Americans were only coming to learn about the events of Kenosha, WI.

We are also interested in secondary analysis exploring heterogeneity on the following categories of traits/characteristics:

- Age
- Level of baseline knowledge and health-preserving behaviors
- Place of residence (correlated with political affiliation, COVID-19 policies and phased reopenings, and socio-economic characteristics)

Given the many ways to cut the data for this secondary analysis, we will follow the methodology of Chernozhukov et al (2019) for this latter set of potential heterogeneous treatment effects.⁵

6. Robustness

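### Section 5.3 tests each lead regression on five or more outcomes in two or three respondent samples, with no stated alpha, primary outcome or multiplicity control

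*Combined protocol and SAP*

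**What the plan says.** Section 5.2 introduces its outcomes with "We intend to measure the treatment effects on the following set of outcomes". It has seven numbered items. Counting the three knowledge indicators separately and policy evaluation once, that is nine outcomes. None is called primary.

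Section 5.3 opens with "We will perform different regression analyses to test the hypotheses listed above". Its default begins "Unless otherwise noted, we will examine treatment effects on knowledge of COVID symptoms", and the full default list is "knowledge of COVID symptoms, knowledge of COVID transmission, intended donation to a COVID-related charity, willingness to pay for masks, changes in reported behavior". For hypothesis 5 it adds one: "we will also analyze effects on allocated donations to black-specific versus race-agnostic COVID-related charities". Section 3 also expresses interest, under hypothesis 5, in perceptions of state and federal policy.

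Most lead regressions come with alternates. Section 5.3 says of the lead tests that "we could also execute the same tests in the full sample, but with more treatment interactions", and footnote 3 says the full-sample versions may sometimes be preferable. Hypothesis 2 also has two alternate definitions of concordance, and a pooled test that is run only for outcomes where the black and white coefficients share a sign.

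Section 5.4 does recognise the problem, but for other analyses. "Given the many ways to cut the data for this secondary analysis", it adopts a published machine-learning method for age, baseline knowledge and behaviour, and place of residence.

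**The concern.** Sections 5.2 and 5.3 contain no alpha, hierarchy, outcome family or adjustment for the main hypotheses. Two of the questions are framed so that a single positive outcome could seem to answer them: hypothesis 1 asks whether the messaging has any effect, and hypothesis 3 whether the acknowledgement matters for any outcome. With five or more separate tests and no decision rule, the reader of a positive result cannot tell how much of it is chance.

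The family is also partly undefined. Transmission knowledge, named in Section 5.3, matches no single indicator in Section 5.2, which defines symptoms, prevention and asymptomatic infection. Link clicks are a key outcome in Section 5.2 but are missing from the Section 5.3 default list. At stake is whether findings on concordance, acknowledgement or disparity content can be taken at their reported p-values.

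**Working it through.** The plan gives no error rate, so there is no figure of its own to reproduce. Alpha of 0.05 two-sided is an assumption, with 0.01 to 0.10 as the range. The correlation between outcomes is also assumed, from 0 to 0.7.

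**Count of lead tests** (samples as listed in Section 5.3):

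| Hypothesis | Samples per lead regression | Regression-samples | Outcomes | Tests |
|---|---|---|---|---|
| 1 | 3 | 3 | 5 | 15 |
| 2 | 2 | 2 | 5 | 10 |
| 3 | 3 + 2 | 5 | 5 | 25 |
| 4 | 2 + 2 | 4 | 5 | 20 |
| 5 | 3 + 3 + 3 + 2 | 11 | 5 or 6 | 55 or 66 |
| Total | | 25 | | 125 or 136 |

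**Expected false positives** = tests × alpha if every null is true, whatever the dependence between tests.
- Alpha 0.05: 125 × 0.05 = 6.25; 136 × 0.05 = 6.8.
- Alpha 0.01: 1.25 to 1.36. Alpha 0.10: 12.5 to 13.6.
- The two alternate concordance definitions add 4 regression-samples, or 20 tests: 145 to 156 tests, 7.25 to 7.8 expected.
- Section 3 limits hypothesis 3a to the two race samples and stresses them for 5b and 5c. On that reading there are 25 − 3 = 22 regression-samples and 22 × 5 = 110 tests, or 13 × 5 + 9 × 6 = 119. That gives 5.5 to 5.95 expected.

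**Familywise error, one regression in one sample.** Independent outcomes: 1 − 0.95^k. Correlated outcomes: simulated with equal correlation ρ.
- k = 5: 1 − 0.95^5 = 22.6%; 21.0% at ρ = 0.3, 18.3% at 0.5, 14.8% at 0.7.
- k = 6: 1 − 0.95^6 = 26.5%; 24.2% at ρ = 0.3, 20.8% at 0.5, 16.4% at 0.7.

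**Familywise error per numbered hypothesis.** Simulated with black and white samples as equal independent halves, the pooled statistic as their sum divided by √2, and the regressions within a hypothesis independent.
- Independent outcomes: H1 46%, H2 40%, H3 68%, H4 64%, H5 94%.
- ρ = 0.5: H1 38%, H2 34%, H3 58%, H4 55%, H5 88%.

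**Sign-dependent pooled test (hypothesis 2).** Under the null the two signs agree half the time. The simulated chance that signs agree and the pooled statistic exceeds 1.96 is 4.89%. Given agreement, the error is therefore 0.0489 / 0.5 = 9.8%, not 5%.

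**Cost of adjustment.** Ratio of detectable effects under Bonferroni, with 80% power assumed: (z[1 − 0.025/k] + 0.84) / (1.96 + 0.84).
- k = 5: (2.576 + 0.84) / 2.80 = 1.22.
- k = 6: (2.638 + 0.84) / 2.80 = 1.24.
- k = 7: (2.690 + 0.84) / 2.80 = 1.26.
- k = 8: (2.734 + 0.84) / 2.80 = 1.28.
- k = 9: (2.773 + 0.84) / 2.80 = 1.29.

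**The case against.** The sponsor can fairly say four things.

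First, the plan is silent on alpha. It does not say that tests will be unadjusted at 5%, or that one significant outcome will be reported as support for a hypothesis. A reader might infer both, but the documents contain neither rule. What stands is the silence itself, in a document meant to fix these choices in advance.

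Second, the expected count needs every null to be true. That is implausible for hypothesis 1, which supplies 15 of the 125 tests: video T1 tells viewers the symptoms on which they are later scored. The realised number of false positives would then be lower.

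Third, the five outcomes are a default, and some differences between Sections 5.2 and 5.3 are deliberate. The race-specific donation belongs to hypothesis 5, and policy evaluation is tied to the disparity content. The real mismatch is narrow: link clicks and the transmission label. The plan also combines several safety behaviours into one index, which already reduces the number of tests.

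Fourth, a reader might infer that the interaction hypotheses are the most prone to chance findings. The calculation does not show that. A true null has the same 5% error whether it concerns a main effect or an interaction. An argument from low power would be a different one, and the plan gives no power figures on which to base it.

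These points limit the claim. They do not supply the missing alpha, family or adjustment.

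**Conclusion.** The gap is real and worth closing before analysis. At an assumed two-sided 5%, one lead regression in one sample carries about 23% familywise error over five independent outcomes (18% at correlation 0.5), and about 26% (21%) over six. The lead tests together give 6.25 to 6.8 expected false positives if all nulls hold.

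Two stronger readings should be avoided. The 18-26% range is not a rate per numbered hypothesis. Each hypothesis covers 2 to 11 regression-samples, and its rate is about 34-94% under the simulation's assumptions. Nor is 6.25 to 6.8 a count for the whole plan. It leaves out the alternate specifications and concordance definitions, the remaining key outcomes, and the Section 5.4 analyses, including the before-and-after Kenosha split.

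The percentages and counts rest on the assumed alpha, and the familywise figures on the assumed correlations. The absence of any stated control does not.

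**What to change.** In Section 5.3:

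1. State alpha.
2. Fix the outcome family per hypothesis: the five defaults for hypotheses 1 to 4, plus the race-specific donation and policy evaluation for hypothesis 5. Say whether state and federal evaluation count once or twice. Map the transmission label to the Section 5.2 indicators, and say whether link clicks belong. Imposing the whole Section 5.2 list on every hypothesis would cost power for no gain.
3. Name one confirmatory specification per hypothesis that matches its stated contrast, and label the others sensitivity analyses. For hypothesis 3a this is the AMARacism × COVID Video interaction. The lead regression uses only COVID-video groups and cannot separate that interaction from a level effect of the AMA statement, which footnote 4 considers likelier than a level effect of doctor concordance. Hypothesis 4a builds on 3a and needs the same check.
4. Within each regression and respondent sample, control familywise error across the family with a Westfall-Young or Romano-Wolf step-down procedure, bootstrap-based for interaction terms. Report unadjusted p-values alongside and base conclusions on the adjusted ones.
5. State that this controls error within each regression and sample, not plan-wide. With 25 such families at 5%, up to 25 × 0.05 = 1.25 would still be expected to reject falsely if every null is true.
6. Label the sign-dependent pooled test of hypothesis 2 as exploratory; step 4 does not correct that selection.

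This is a cheap improvement: plan wording and a resampling step. The downside is a detectable effect larger by at most about 22-24% for five or six outcomes under Bonferroni, about 26-28% if the hypothesis 5 family has seven or eight, and 29% for nine. Step-down on correlated outcomes costs less. The hypothesis 3a interaction will also be estimated less precisely than the within-treated contrast; the text gives no allocation shares from which to size that loss.

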2.2 Recruitment and Sampling

We are using Lucid to recruit a sample and to compensate subjects for their participation. Our total target sample size is 20,000 subjects, 10,000 African American respondents, and 10,000 White American respondents. We require all participants to be age 18 or older, and we are targeting individuals who have *not* completed a college degree.

Figure 1: Treatment Design

Note: There are 5 randomization instances summarized in this diagram. For the fully extended tree with all 24 final individual cells, see Figure 2.

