6.1 Threats to Interpretation

We would like to assume that differences across videos come from either differences in the racial identity of the doctors in the video or from differences in the content of the messages, rather than from other chance differences across videos. Because we are including both white and black respondents who will be watching the same exact videos, we will be able to include video fixed effects in some specifications.

⁵Chernozhukov, Victor, Mert Demirer, Esther Duflo, and Ivan Fernandez-Val (2019). Generic machine learning inference on heterogeneous treatment effects in randomized experiments. No. w24678. National Bureau of Economic Research.

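### The printed full-sample doctor-concordance models omit the video terms that Section 6.1 offers, and AMA-messenger concordance (H4) has no pooled-race model

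*Combined protocol and SAP*

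**What the plan says.** Section 5.3 item 2 regresses each outcome on doctor concordance and controls X, by respondent race. Where the two coefficients have the same sign, "we will estimate the above equation again in the full sample". On X, "we will use a double-lasso procedure to select regression controls", plus availability for follow-up. Neither doctor race, video nor respondent race is named as a forced term.

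Section 5.3 item 5 asks "are race-concordant doctors more effective messengers about racial disparity" and fits doctor concordance by disparity message in Black, white and all respondents, again with no doctor-race or video term.

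Section 5.3 item 4 (H4) studies concordance of the AMA messenger in "Individuals receiving an AMA message about racial injustice and a treatment message about COVID. Separate analysis for black and white respondents". Section 3 item 4 also restricts H4 to separate tests by race. An optional alternate specification brings in the control videos and both AMA statements, with a COVID video × AMA concordance × AMA racism term. It adds treatment arms and is not described as pooling the races.

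Section 6.1 says the authors want to attribute differences to messenger race or message content rather than to chance differences between videos. Because both races watch the same videos, "we will be able to include video fixed effects in some specifications". It does not say which.

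On numbers, Section 2.2 states: "Our total target sample size is 20,000 subjects, 10,000 African American respondents, and 10,000 White American respondents".

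**The concern.** Having both races view the same recordings is what lets this design separate concordance from the particular recording. A better-delivered video by a Black messenger looks like a positive concordance effect in Black respondents and a negative one in white respondents. Only a model that uses both races can take that difference out.

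The plan sees the threat but does not carry the remedy into its equations. For the AMA messenger no pooled-race model is printed, so a recording difference could be reported as AMA concordance in one race. For the doctor, the pooled equations are protected only while the two races contribute equal numbers. Section 4.2 excludes very fast respondents without a stated threshold, and Section 6.2 expects modest recontact and high attrition for the follow-up outcomes, so equal analysed numbers are not assured.

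**Working it through.** **Design check.** Two AMA statements × two AMA-messenger races × two doctor races × three video contents (placebo, COVID, COVID plus disparities) = 24, which agrees with "For the fully extended tree with all 24 final individual cells, see Figure 2". The race targets sum to 20,000. The plan states no power or effect size to reproduce. I assume equal cells within race, 1:1 messenger allocation and outcome SD 1; the allocation figures are not available.

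**One race at a time.** Write Y = c·Concord + v·BlackMessenger.
- Black respondents: Concord = BlackMessenger, so the coefficient is c + v.
- White respondents: Concord = 1 − BlackMessenger, so the coefficient is c − v.

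So v is half the gap between the race-specific effects. A video fixed effect is collinear with concordance in either race alone.

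**H4 main equation.** COVID video plus racial-injustice statement: 10,000 × 2/3 × 1/2 = 3,333 per race. SE = 2/√3,333 = 0.0346. Set c = 0.
- v = 0.05 SD: z = 0.05/0.0346 = 1.44; rejection probability 0.303 per race; at least one race 1 − (1 − 0.303)² = 0.514.
- v = 0.10 SD: 0.823 per race; at least one race 0.969.
- v = 0: 1 − 0.95² = 0.0975, the correct benchmark for two tests.

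**H4 alternate specification.** Per race, the triple interaction contrasts four COVID groups of 10,000 × (2/3)/4 = 1,667 and four placebo groups of 10,000 × (1/3)/4 = 833. SE = √(4/1,667 + 4/833) = 0.085. It removes a recording difference that is additive, meaning the same with and without the COVID video, at about 2.5 times the SE of the main equation (0.085/0.0346).

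**Pooled doctor models as printed.** With race shares wB and wW, Cov(Concord, BlackDoctor) = 0.25(wB − wW) and Var(Concord) = 0.25, so the pooled coefficient is c + (wB − wW)v.

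| Black:white analysed (assumed) | Share of v absorbed, in size |
|---|---|
| 50:50 (planned) | 0% |
| 48:52 | 4% |
| 40:60 | 20% |
| 35:65 | 30% |

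Exact weighted least squares at 35:65 with v = 0.10 and c = 0 gives −0.030, with or without respondent race, and 0 once doctor race is added. Doctor concordance × disparity message in item 5 absorbs the same share of doctor race × disparity message. In item 2, the same-sign rule requires c + v and c − v to agree in sign, so |v| < |c| and leakage is at most |wB − wW| of c.

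**With messenger race and respondent race included.** The concordance coefficient is ½[(c + v) + (c − v)] = c at any split. SE inflation is 1/√(1 − (wB − wW)²): 1.00 at 50:50, 1/√0.96 = 1.02 at 40:60, 1/√0.91 = 1.05 at 35:65. For a pooled H4 model at 50:50, SE = 2/√6,667 = 0.0245.

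**The case against.** Much can be said for the plan.
- A reader might infer that the pooled doctor-concordance estimates are biased as designed. They are not: at the planned equal numbers the leakage is exactly zero. No document gives a 40:60 or 35:65 split, and the same-sign rule caps the leakage in item 2.
- A reader might infer that the plan overlooks differences between videos. Section 6.1 raises them and names fixed effects. Since these cannot be fitted with concordance in one race, they can only be meant for pooled models. What is missing is which ones.
- A reader might infer that H4 never gets an estimate free of the recording. The alternate specification does remove additive recording differences. It is optional and imprecise, but it is printed.
- Both race-specific coefficients are planned, so their mean, which equals the corrected coefficient, can be computed from planned output. Section 5.4 also calls differences in concordance effect by respondent race central, though it gives no equation.
- A pure recording difference gives opposite signs in the two races, side by side. At 0.05 SD, both races are significant in the same direction only about 0.02% of the time. Setting 51% against 5% would also overstate the problem; the benchmark is 9.75%.
- v may reflect a true difference in concordance effect by race, and a share-weighted average is then a legitimate pooled target.

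All of this stands, and it limits the point. It does not supply a stated pooled estimate and standard error for AMA concordance, and it does not say which doctor models carry the video terms.

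**Conclusion.** The point holds in a limited form. Section 6.1's aim is not carried into the printed equations: the full-sample doctor models in items 2 and 5 have no doctor-race or video term, and H4 has no pooled-race model.

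H4 is the stronger part, because it does not depend on race imbalance. Each main-equation coefficient mixes concordance with the recording, and under the stated assumptions a 0.05 SD recording difference gives a significant result in at least one race 51% of the time, against 9.75%. The pooled doctor models are a safeguard issue: no effect at 50:50, and 20% of half the race-specific gap at an assumed 40:60.

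The 0.05 SD difference, the unequal splits, the equal cells and the 1:1 messenger allocation are all assumptions. The change is worth making because it is nearly free and serves the plan's own aim. It does not show that the planned analysis is invalid.

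**What to change.** Amend Section 5.3 and name in Section 6.1 the models that carry video terms.
1. In the pooled doctor-concordance models of items 2 and 5, force in respondent race and doctor race (or video fixed effects). In item 5 also force in doctor race × disparity message.
2. Add to H4 a pooled AMA-concordance model in those seeing a COVID video and the racial-injustice statement, with respondent race and AMA-messenger race forced in. Report it beside the race-specific coefficients.
3. State that the pooled coefficient is the equal-weight mean of the two race-specific effects.
4. Reconcile Section 2.3, where scripts are adapted by racial group, with Section 6.1, where both races see identical videos. The remedy needs identical videos.

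The cost is plan wording and a few regressions on data already being collected. The standard error rises by 0% at 50:50, 2% at 40:60 and 5% at 35:65.

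This does not repair the all-messenger and any-messenger definitions in item 2, or the AMA concordance × doctor concordance term in H4. An effect of doctor and AMA messenger being of the same race stays mixed in there, and the plan should say so.
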